7. RISKS

a. Potential Risks

Non-invasive visual stimulation procedures frequency - Overall 40 sessions within 8 weeks. Each session around one hour. severity - The visual stimulation procedure will be no more severe than viewing content through any of the currently commercially available Virtual Reality systems, such as the Oculus Rift (<https://www3.oculus.com/en-us/rift/>), or the HTC Vive (<https://www.amazon.com/HTC-VIVE-Virtual-Reality-System-Pc/dp/B00VF5NT4I>), or the magic leap's system (<https://www.magicleap.com/>) There is a risk of experience motion sickness, however the investigators have reduce this at minimum, by ensuring that there is minimal, if any, mismatch of vergence-accommodation and visual proprioceptive cues. reversibility - We do not expect the commercially available VR system we shall use to produce any undesirable effect in any form. Other procedures will be BCVA, HVF, OCT that are usually performed at the clinic as standard of care and possess minimal risk. Risks of Eye Examination and Dilation: A combination of eye drops (phenylephrine, tropicamide and proparacaine hydrochloride) will be used to widen your pupils. These drugs are used routinely in any dilated fundus exam in an ophthalmologist's clinic. It is likely that your eyes may be sensitive to light after they are dilated, but wearing sunglasses helps this, and it will decrease in a matter of hours after you receive the drops. If you find it difficult to drive after receiving dilating eye drops, you should arrange for transportation home after the testing. You may experience temporary glare and blurry vision when eyes are dilated.

Risk of Optical Coherence tomography (OCT) There are no known risks associated with OCT. Risk of Visual field test There are no known risks associated with visual field test.

b. Procedures to Minimize Risk

We plan to use commercially available Virtual Reality hardware, which goes through the standard safety protocols for testing before being available in the mass market. The investigator will keep the participant under active observation at all times during the VR sessions, and will discontinue promptly if the participant feels discomfort at any point. All confidential information will be kept in password-protected Stanford owned computers, accessible only to the investigators registered in this protocol.

c. Study Conclusion

In the event of premature withdrawal from the study, the termination date will be the last date the subject is seen at the clinic or the date of the last telephone contact with the subject.

d. Data Safety Monitoring Plan (DSMC)

i. Data and/or events subject to review

Adverse events, protocol deviations, aggregate data analysis reports, progress toward study endpoint(s), participant consent forms.

ii. Person(s) responsible for Data and Safety Monitoring

The Protocol Director.

e. Risks to Special Populations

We will utilize current available VR system that has been already recommended to be used in children 13 years old and older. The Oculus Rift and Samsung's Gear VR headsets are recommended for ages 13+, while Sony's recommendation for its PlayStation VR is ages 12 and up. And Google cardboard headset should be used by kids under adult supervision. The headsets that we will be using will be similar to the current available on the market (Oculus Rift and Samsung's Gear VR headsets), while they use it, they will be sitting and under adult supervision.

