2. STUDY PROCEDURES

a. Procedures

Screening visit will include eye exam, best corrected visual acuity (BCVA), Humphrey visual field test (HVF), and Ocular Coherence Tomography (OCT), all these tests will be performed as standard of care. Baseline visit will include HVF and VFQ25. VFQ25 could be also applied at screening visit. After subject complete Screening and Baseline visit within 8 weeks, the subject will be trained on how to do VR stimulation. And will be provided a VR headset to take home. The VR or VR stimulation will consist in up to 1 hour per day session that will be done at home Monday through Friday for 12 weeks and the following week BCVA, HVF will be performed. The following week the study subject will start another cycle of 12 weeks of VR stimulation and the following week, will repeat test (BCVA, HVF) and so until the study subject complete up to 8 cycles. At

least 8 weeks after completing the last cycle subject will do HVF, OCT, BCVA and VFQ25. VR 1-hour sessions will consist of an exposure to a non-invasive visual stimulation where the subject will be sitting wearing a VR headset. After subjects complete 52 weeks of VR stimulation (4 cycles) they will be able to continue for another 52 weeks (4 cycles), or stop the VR stimulation and we will follow them doing only the testing (Visual acuity, Visual field test, OCT) every 12 weeks for another 12 months. The VR or VR stimulation will be performed as part of research, at no cost, HVF, OCT an eye exam will be considered standard of care and billable to subject insurance.

b. Procedure Risks

The VR stimulation is a designed computational model developed by Stanford University researchers, this model aims to maximize the activity of the neurons in the retina, and it will pose no more than minimal risks involved with using any of the currently commercially available Virtual Reality platforms, such as the Oculus Rift (<https://www3.oculus.com/en-us/rift/>), or the HTC Vive (<https://www.amazon.com/HTC-VIVE-Virtual-Reality-System- Pc/dp/B00VF5NT4I>), or the magic leap's system (<https://www.magicleap.com/>). BCVA, HVF and OCT tests are currently performed at the clinic for regular patient care, and will be used to measure any structural or functional change. The VFQ-25 will also tell us if there is any significant impact in the quality of life/vision of the study subjects.

c. Use of Deception in the Study

No deception will be used.

d. Use of Audio and Video Recordings

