No audio or video recording will take place.

e. Alternative Procedures or Courses of Treatment

There are alternative treatments available for glaucoma including drug therapy and surgery that are used to reduce the intraocular pressure. Participants will be able to continue their current glaucoma treatment during their participation in the study and get any of these treatments as needed.

f. Will it be possible to continue the more (most) appropriate therapy for the participant(s) after the conclusion of the study?

Yes

g. Study Endpoint(s)

Primary and secondary efficacy endpoints will be measured by:

-Change in visual field by any one of the following three indices:

1. Visual Field Index(VFI)
2. Meand Deviation (MD)
3. Pointwise linear regression (PLR) analysis

-Change in the OCT: retinal nerve fiber layer (RNFL), change in ganglion cell layer, changes in other retina cell layers

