6. PARTICIPANT POPULATION

a. Planned Enrollment

200 subjects with glaucoma or other retinal diseases or disorders of the visual system 100 normal controls (patients with normal vision) General population, above the age of 12, willing to take part in our study, with glaucoma or other retinal diseases or disorders of the visual system or normal controls. All subjects will be recruited at Byers Eye Institute Stanford University

b. Age, Gender, and Ethnic Background

Age >12 both sexes will be recruited. Any ethnic background.

c. Vulnerable Populations

No potentially vulnerable subjects will be actively recruited into this study.

d. Rationale for Exclusion of Certain Populations

Children 12 years old and older will be included in the study. Current VR systems have proven to be safe on children 12 years and older.

e. Healthy Volunteers

100 patients with normal vision (healthy volunteers) will be recruited for the study, as long as they satisfy screening, inclusion and exclusion criteria.

The participants will be exposed to no more than minimal risk, associated with watching media on currently commercially available Virtual Reality platforms, such as the Oculus Rift (<https://www3.oculus.com/en-us/rift/>), or the HTC Vive (<https://www.amazon.com/HTC-VIVE-Virtual-Reality-System-Pc/dp/B00VF5NT4I>), or the magic leap's system (<https://www.magicleap.com/>). Additionally, to protect the welfare of the participants, they will be clearly told in the informed consent, which they will sign before entering the study, that they are free to discontinue at any point if they want.

f. Recruitment Details

Participants will be identified from the Stanford Healthcare clinic population at the Byers Eye Institute at Stanford who meet the inclusion criteria. Participants who are identified during chart review will be notified of their eligibility, after the patient's physician has previously notified the potential research participant and obtained approval to be contacted.

g. Eligibility Criteria

i. Inclusion Criteria

For subjects with glaucoma, other retinal diseases, or disorders of the visual system:

1. Patient age > 12 years
2. Compliance with investigator instructions, tests and visit during subject participation in the study.
3. Sufficient fixation ability
4. Best corrected visual acuity of 20/200 or better in at least one eye, or capable to see the visual stimulus at least in one eye.

For healthy volunteers:

1. Patient age > 12 years

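### Section 7b promises investigator observation of every VR session, but Section 2a has the sessions done at home with no means of observation described; the exposure in 7a (40 sessions in 8 weeks) also contradicts 2a

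*Protocol*

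**What the plan says.** **Observation.** Section 7b lists the measures that reduce risk. One of them is a commitment by the investigator: "The investigator will keep the participant under active observation at all times during the VR sessions". The same sentence has the investigator stop the session without delay on any discomfort. It is not limited to the training session or to any part of the course.

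**Where sessions take place.** Section 2a says the participant is trained and then "And will be provided a VR headset to take home". Stimulation is "up to 1 hour per day session that will be done at home Monday through Friday for 12 weeks", followed by a test week, and this is repeated for up to eight cycles. The first four cycles take 52 weeks. After that the participant may do four more, or stop stimulation and be tested every 12 weeks for another 12 months.

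**Exposure in the risk section.** Section 7a gives the frequency as "Overall 40 sessions within 8 weeks. Each session around one hour".

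**Other relevant text.** Section 2d states: "No audio or video recording will take place". Section 7e mentions an adult supervising use of the headset, in the paragraph on children. Section 6l puts active participation at 24 months. Section 6e says of the risk: "The participants will be exposed to no more than minimal risk". Section 4 classes the VR software as not significant risk.

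**The concern.** Section 7b names three measures: commercially tested hardware, observation by the investigator, and confidential data handling. Only observation acts while a session is under way. Under 2a the sessions happen in the participant's home and nothing says how the investigator would watch them. A reader of the risk section would believe that someone on the study team is present to stop a session when the participant feels unwell. A reader of the procedures would find nobody assigned to do so. The study also admits minors over 12. Taken literally, each unobserved home session departs from 7b, and protocol deviations are among the items reviewed under 7d.

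The exposure figure compounds this. The risk section is where exposure is weighed against safeguards, and it describes a short, observed course when 2a describes a long course at home.

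**Working it through.** **Part 1: observation. The two sections side by side.**

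| Question | Section 7b | Section 2a |
|---|---|---|
| Who is with the participant? | The investigator, throughout every session | Nobody named |
| Where? | Not stated | At home, with a headset taken home |
| Who stops the session on discomfort? | The investigator | Not stated |

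Three readings might reconcile them:

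1. *Live remote viewing.* Section 2d excludes recording only, so live viewing is not ruled out. No section mentions it.
2. *The supervising adult in 7e.* That text sits in the paragraph on children and does not refer to the investigator. It cannot stand in for the 7b commitment for adult participants.
3. *7b covers only the training session.* Its wording covers the VR sessions without any such limit.

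None of the three is supported by the text, so the conflict stands.

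**Part 2: exposure.**

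Inputs: 5 sessions a week (Monday to Friday, 2a); 12 stimulation weeks per cycle (2a); 4 cycles in the first year and at most 8 in all (2a); 40 sessions in 8 weeks (7a).

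The 7a figure is consistent within itself: 5 per week × 8 weeks = 40. The weekly rate matches 2a, so the disagreement is over duration and total.

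Sessions under 2a = 5 × 12 × number of cycles:

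| Cycles | Sessions | Ratio to 40 | Stimulation weeks | Weeks with test weeks (13 per cycle) |
|---|---|---|---|---|
| 1 | 60 | 1.5 | 12 | 13 |
| 4 | 240 | 6 | 48 | 52 |
| 8 | 480 | 12 | 96 | 104 |

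A single cycle already exceeds both the 40 sessions and the 8 weeks. If the 52 and 104 weeks are read as unbroken stimulation, the totals are 52 × 5 = 260 and 104 × 5 = 520, and the contradiction remains. The 8-week periods that do appear in 2a are the screening and baseline window and the minimum gap before final testing. Neither is a stimulation period.

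**Which section is the operative one?** Four cycles of 13 weeks give 52 weeks, which matches the duration that 2a states for four cycles. The 24 months in 6l fits either path in 2a: eight cycles (8 × 13 = 104 weeks), or four cycles plus 12 months of testing only. It does not show which path is meant, but it cannot fit an 8-week course. Section 7a is therefore the one to correct.

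**The case against.** Both contradictions are hard to dispute, so the case on the other side is about weight.

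- *Observation is undescribed, not impossible.* This is right. Since 2d bars only recording, the supportable statement is that no means of observing home sessions is given.
- *Minors are the group already covered.* Section 7e provides for an adult to supervise them. This has force: the larger gap is for adults at home. It does not rescue 7b, which names the investigator and covers all participants.
- *The 24 months in 6l does not prove eight cycles.* Correct, as the working shows. It still excludes an 8-week course, which is all that is needed.
- *The 12-fold ratio is an optional maximum.* Also correct. The ratio that applies to every participant who completes the first year is 6. Actual adherence does not change the point, because 7a states the planned exposure.
- *The session count is a minor wording error.* The weekly rate and session length are close in both places, and the risk argument rests on comparison with commercial VR viewing, not on a total. This is fair for 7a alone, which is the lesser part of the point. The 7b commitment is a participant protection and carries more weight.
- *A symptom question is a new procedure.* It goes a little beyond reconciling the text. It is proposed because, once investigator observation is withdrawn, something should carry discomfort at home into the adverse event review in 7d.

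**Conclusion.** The point holds in both parts. The observation promised in 7b has no described means of delivery under the home procedures in 2a, and the exposure in 7a is wrong on any reading of 2a: 40 sessions stated, against 60 per cycle, 240 over four cycles and up to 480 over eight. These totals assume every scheduled session is done. They are counts of sessions, and no claim is made that risk rises in proportion.

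This should be fixed, but the consequence is limited. The protocol describes the risk as minimal, motion sickness is the only VR harm it names, and participants are told they may discontinue whenever they wish. Section 2a is clear about what is to be delivered, and no efficacy endpoint is affected. No claim is made about missing contact or reporting details, since the contact and consent pages are not part of the document at hand.

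**What to change.** 1. **Section 7a.** Replace the exposure with the 2a schedule: up to 1 hour a day, 5 days a week, 60 sessions per 12-week cycle, 240 over four cycles and up to 480 over eight.
2. **Section 7b.** Replace the observation sentence with a safeguard that works at home. The participant, or for a minor the supervising adult in line with 7e, stops the session at once on discomfort and reports it to the study team.
3. **Symptom question.** Ask about symptoms at least at each scheduled test visit, so that events at home reach the review in 7d. Reports between visits are optional.
4. **Alternative.** If live observation is intended, keep 7b and describe in 2a how it is done.

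**Cost.** Items 1 and 2 are a wording amendment to 7a, 7b and any consent text that repeats them. Item 3 takes a little staff time at visits already planned: 4 in the first year, up to 8 over eight cycles, plus the visit at least 8 weeks after the last cycle. No extra patients or visits and no limit on dosing are needed.

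The alternative is far more expensive. With one observer per session, full enrolment and full adherence, four cycles take up to 240 × 1 h = 240 staff hours per participant. That is up to 200 × 240 = 48,000 hours for the planned patients, or 300 × 240 = 72,000 if the 100 controls also complete four cycles. These are upper bounds, given only to compare the two routes.

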8. BENEFITS

The participants may improve their visual acuity and visual field. The knowledge gained from this study can be combined in future with other therapies in patients suffering from lack of vision arising from glaucoma or other retinal diseases, as well as disorders of the visual system.

9. PRIVACY AND CONFIDENTIALITY

All participant information and specimens are handled in compliance with the Health Insurance Portability and Accountability Act (HIPAA) and privacy policies of Stanford University, Stanford Health Care, and Stanford Children's Health.
